5.2.3 Second Course

All subjects who stop pembrolizumab treatment with CR may be eligible for up to an additional 12 months (17 cycles) of pembrolizumab treatment if they progress after stopping pembrolizumab from the initial treatment phase. This retreatment is termed the Second Course Phase of this trial and is only available if the trial remains open and the subject meets the following conditions:

Either

- Stopped initial treatment with pembrolizumab after attaining an investigator-determined confirmed CR based on the RECIST 1.1, and
 - Was treated with at least 8 cycles of pembrolizumab before discontinuing treatment, and
 - Received at least 2 cycles of pembrolizumab beyond the date when the initial CR was declared

OR

- Had CR and stopped pembrolizumab treatment after completion of 24 months (35 cycles) of pembrolizumab for reasons other than disease progression or intolerability

AND

- Experienced an investigator-determined radiographic disease progression by the RECIST 1.1 after stopping initial pembrolizumab treatment, and
 - No new anticancer treatment was administered after the last dose of pembrolizumab, and

- The subject meets all of the safety parameters listed in the inclusion criteria and none of the safety parameters listed in the exclusion criteria, and
- The study is ongoing

An objective response or disease progression that occurs during the Second Course Phase for a subject will not be counted as an event for the primary analysis of either endpoint in this trial.

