- When symptoms improve to Grade 1 or less, steroid taper should be started and continued over no less than 4 weeks.

- **T1DM if new onset (including diabetic ketoacidosis) or \geq Grade 3 hyperglycemia if associated with ketosis (ketonuria) or metabolic acidosis**

- For **T1DM** or **Grade 3–4 Hyperglycemia**
 - Insulin replacement therapy is recommended for T1DM and for Grade 3–4 hyperglycemia associated with metabolic acidosis or ketonuria.
 - Evaluate patients with serum glucose and a metabolic panel, urine ketones, glycosylated hemoglobin, and C-peptide.

- **Hypophysitis:**

- For **Grade 2 events**, treat with corticosteroids. When symptoms improve to Grade 1 or less, steroid taper should be started and continued over no less than 4 weeks. Replacement of appropriate hormones may be required as the steroid dose is tapered.
- For **Grade 3–4 events**, treat with an initial dose of IV corticosteroids followed by oral corticosteroids. When symptoms improve to Grade 1 or less, steroid taper should be started and continued over no less than 4 weeks. Replacement of appropriate hormones may be required as the steroid dose is tapered.

- **Hyperthyroidism or Hypothyroidism:**

Thyroid disorders can occur at any time during treatment. Monitor patients for changes in thyroid function (at the start of treatment, periodically during treatment, and as indicated based on clinical evaluation) and for clinical signs and symptoms of thyroid disorders.

- **Grade 2** hyperthyroidism events (and **Grade 2–4** hypothyroidism):
 - In hyperthyroidism, non-selective beta-blockers (e.g., propranolol) are suggested as initial therapy.
 - In hypothyroidism, thyroid hormone replacement therapy with levothyroxine or liothyronine is indicated per standard of care.
- **Grade 3-4** hyperthyroidism
 - Treat with an initial dose of IV corticosteroid followed by oral corticosteroids. When symptoms improve to Grade 1 or less, steroid taper should be started and continued over no less than 4 weeks. Replacement of appropriate hormones may be required as the steroid dose is tapered.

- **Hepatic:**

- For **Grade 2** events, monitor liver function tests more frequently until returned to baseline values (consider weekly).
 - Treat with IV or oral corticosteroids
- For **Grade 3–4** events, treat with IV corticosteroids for 24 to 48 hours.
- When symptoms improve to Grade 1 or less, a steroid taper should be started and continued over no less than 4 weeks.

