b. Within 7 days prior to Day 0 of ADV/HSV-tk. Only screening procedures not performed within 7 days of ADV/HSV-tk dosing are required at baseline.

c. The baseline symptom-medical history and physical examination are not required if the screening medical history and physical examination were conducted within 7 to 28 days prior to Day 0 of ADV/HSV-tk. Vital sign (blood pressure, respiratory rate, pulse, and oral temperature) measurements will be performed at each physical exam.

d. A 12-lead ECG will be performed at screening, at EOT, and when clinically indicated. MUGA scan or echocardiogram will be performed only if clinically indicated.

e. A blood sample for CBC with platelet count and differential WBC count will be obtained at screening, on Days 0 and 17, every 3 weeks thereafter until completion of the protocol-specified treatment, at EOT, and when clinically indicated.

If a patient is found to have an ANC $< 1.5 \times 10^9/L$, platelet count $< 100 \times 10^9/L$, or both, the CBC with differential should be repeated at least every other day until the ANC and platelet count have exceeded these values.

A blood sample for clinical chemistry panel (albumin, glucose, sodium, potassium, carbon dioxide, chloride, calcium, BUN, creatinine, total bilirubin, total protein, alkaline phosphatase, AST, and ALT) and evaluation of phosphorus, magnesium, and LDH will be obtained at screening, on Days 0 and 17, every 3 weeks thereafter until completion of the protocol-specified treatment, at EOT, and when clinically indicated. PT/INR and aPTT will be tested at screening and on Day 17. TSH, free T4, and total T3 will be tested at screening and when clinically indicated.

f. Urinalysis (blood, glucose, protein, specific gravity) will be performed at screening and when clinically indicated.

g. For women of childbearing potential, the results of a serum β -hCG pregnancy test must be negative within 7 days before the first treatment dose is administered. If the screening serum β -hCG pregnancy test is performed more than 7 days before ADV/HSV-tk dosing, it must be repeated at baseline, with results known to be negative prior to the first dose of the study treatment. Testing is to be repeated as clinically indicated.

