tumors will be treated with a short course (5-8 fractions) of three-dimensional RT. SBRT and three-dimensional RT will be administered over 2 weeks from Day 2 to Day 16 of the study. Pembrolizumab at a dose of 200 mg will be intravenously infused over 30 min Q3W (\pm 1 day) starting on Day 17 (\pm 1 day) of the study and continuing until disease progression, unacceptable toxicity, or up to 24 months (35 cycles) in subjects without disease progression. All subjects who stop pembrolizumab treatment with complete response may be eligible for up to an additional 12 months (17 cycles) of pembrolizumab treatment if they progress after stopping pembrolizumab from the initial treatment phase. The subject must meet the conditions outlined in Section 5.2.3.

m. AEs and SAEs will be captured from the time of informed consent signing up to 30 days after the final dose of pembrolizumab. Study treatment-related SAEs and any study patient death occurring beyond 30 days after the last dose of pembrolizumab should also be reported.

*Patients will be treated until disease progression, unacceptable toxicity, or up to 24 months in subjects without disease progression.

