7.1.2.7.1 Second Course (Retreatment) Tumor Imaging

Tumor imaging must be performed within 4 weeks prior to restarting treatment with pembrolizumab. The first on-study imaging assessment should be performed at 8 weeks (± 7 days) after the restart of treatment. Subsequent tumor imaging should be performed every 8 weeks (± 7 days) or more frequently, if clinically indicated.

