7.1.3 Laboratory Procedures/Assessments

Details regarding specific laboratory procedures/assessments to be performed in this trial are provided below

Laboratory Safety Evaluations (Hematology, Chemistry, and Urinalysis)

A blood sample for clinical chemistry panel (sodium, potassium, carbon dioxide, chloride, calcium, glucose, albumin, blood urea nitrogen, creatinine, total bilirubin, total protein, alkaline phosphatase, AST, and ALT) and evaluation of phosphorus, magnesium, and lactate dehydrogenase will be obtained at screening, on Days 0 and 17, and every 3 weeks thereafter until completion of the protocol-specified treatment, at EOT, and when clinically indicated. PT/INR and aPTT will be tested at screening and on Day 17. Thyroid-stimulating hormone, free thyroxine, and total triiodothyronine will be tested at screening and when clinically indicated. A blood sample for complete blood count (CBC) with platelet count and differential WBC count will be obtained at screening, on Days 0 and 17, every 3 weeks thereafter until completion of the protocol-specified treatment, at EOT, and when clinically indicated. If a patient is found to have an ANC $< 1.5 \times 10^9/L$, platelet count $< 100 \times 10^9/L$, or both, the CBC with differential should be repeated at least every other day until the ANC and platelet count have exceeded these values. For women of childbearing potential, the results of a serum β -hCG pregnancy test must be negative within 7 days before the administration of the first dose of trial treatment. If the screening serum β -hCG pregnancy test is performed more than 7 days before ADV/HSV-tk dosing, it must be repeated at baseline. Pregnancy testing is to be repeated as clinically indicated. Urinalysis (blood, glucose, protein, specific gravity) will be performed at screening and when clinically indicated. Laboratory tests for hematology, chemistry, urinalysis, and others are specified in Table 5.

Table 5 Laboratory Tests

Hematology	Chemistry	Urinalysis	Other
Hemoglobin	Albumin	Blood	Serum β - hCG†
Platelet count	Alkaline phosphatase	Glucose	PT (INR)
WBC count (total and differential)	ALT	Protein	aPTT
ANC	AST	Specific gravity	Total triiodothyronine
	Lactate dehydrogenase	Microscopic exam (If abnormal)	Free thyroxine
	Carbon dioxide	results are noted	Thyroid-stimulating hormone
	Creatinine		
	Calcium		
	Chloride		
	Glucose		
	Phosphorus		
	Potassium		
	Sodium		
	Magnesium		
	Total bilirubin		
	Total protein		

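### Section 5.4.1 asks for periodic thyroid monitoring on treatment, but the flow chart and Section 7.1.3 schedule no routine thyroid test during up to 35 pembrolizumab cycles

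*Combined protocol and SAP*

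**What the plan says.** Section 5.4.1 (Supportive Care Guidelines) notes that thyroid disorders may arise at any point on treatment and then gives a monitoring instruction with three parts: "Monitor patients for changes in thyroid function (at the start of treatment, periodically during treatment, and as indicated based on clinical evaluation". It also asks for watchfulness for clinical signs and symptoms.

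The assessment schedule is narrower. Footnote e of the flow chart (Section 6.1) states: "TSH, free T4, and total T3 will be tested at screening and when clinically indicated". Section 7.1.3 agrees: "total triiodothyronine will be tested at screening and when clinically indicated". Table 5 lists the thyroid tests without timing, and the flow chart has no thyroid row of its own.

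The same footnote e puts the chemistry panel on a regular schedule after screening: "on Days 0 and 17, every 3 weeks thereafter until completion of the protocol-specified treatment, at EOT, and when clinically indicated". Footnote l describes pembrolizumab as starting on Day 17 "of the study and continuing until disease progression, unacceptable toxicity, or up to 24 months (35 cycles) in subjects without disease progression".

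**The concern.** The instruction in Section 5.4.1 and the schedule that sites will follow do not match. Section 5.4.1 lists periodic testing separately from testing on clinical grounds, so the second cannot stand in for the first. A coordinator working from the flow chart would order no thyroid panel during pembrolizumab unless someone had a reason to ask for one.

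Two things are at stake.

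- **Detection.** Hypothyroidism is the most commonly reported adverse event of special interest in the background data (7.2%, with hyperthyroidism at 2.2%; Section 4.1.1.4.5). Without a routine test, early or asymptomatic change is found when an investigator happens to test. Hyperthyroidism has treatment consequences: Table 3 in Section 5.2.1.2 holds pembrolizumab at Grade 3 and stops it permanently at Grade 4.
- **Reporting.** Section 8.1 promises the frequency of all adverse events and laboratory abnormalities. On-treatment thyroid abnormalities would be ascertained according to individual practice, so asymptomatic ones may be undercounted.

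**Working it through.** The plan states no figure to reproduce. The check compares the texts and then counts tests.

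**1. The three parts of Section 5.4.1 against the schedule**

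| Part of Section 5.4.1 | Matching provision | Met? |
|---|---|---|
| At the outset | Screening test; footnote b: "Only screening procedures not performed within 7 days of ADV/HSV-tk dosing are required at baseline" | Roughly |
| Periodically on treatment | None in footnote e, Section 7.1.3 or Table 5 | No |
| On clinical grounds | Footnote e and Section 7.1.3 | Yes |

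On the first row: with footnote b, the last thyroid test falls 1 to 7 days before Day 0. The first pembrolizumab dose is on Day 17, so the nominal gap is 1 + 17 = 18 to 7 + 17 = 24 days. I treat that as adequate.

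**2. Length of the unscheduled period**

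- Inputs: 35 cycles, one every 3 weeks, first dose on Day 17 (footnote l).
- First to last dose: (35 − 1) × 3 = 102 weeks.
- Nominal day of dose 35: 17 + 34 × 21 = Day 731.
- Routine thyroid tests scheduled in that period: 0.

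**3. Panels added by a stated interval**

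The documents give no interval, so it is an assumption and a range is shown. Counts are for a patient who completes all 35 cycles.

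| Interval | Cycles tested | On treatment | With 1 at EOT |
|---|---|---|---|
| Every cycle | 2 to 35 | 34 | 35 |
| Every second cycle | 3, 5, …, 35 | (35 − 3)/2 + 1 = 17 | 18 |
| Every fourth cycle | 5, 9, …, 33 | (33 − 5)/4 + 1 = 8 | 9 |

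Cycle 3 falls on Day 17 + 2 × 21 = 59, which is already visit V9 with a chemistry draw.

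**4. A more typical patient**

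Mean treatment time is not in the documents. As an assumption, take 3.7 months, the median progression-free survival reported for pembrolizumab in NSCLC (Section 4.1.1.4.1). At 30.4375 days per month this is 3.7 × 30.4375 = 112.6 days, which allows doses on days 0, 21, 42, 63, 84 and 105 after the first, six in all. Testing every second cycle then adds Cycles 3 and 5 plus EOT: 3 panels.

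**The case against.** The strongest reply is that this is a mismatch of wording with little effect on conduct. Section 5.4.1 is itself part of the protocol, is presented as suggested care, and names no interval. Section 7.1 lets investigators add unscheduled procedures when they judge them clinically necessary. Nothing forbids periodic testing, and a site that never does it could be said to overlook Section 5.4.1. The clinical consequence is also modest. Full examinations with vital signs occur every 3 weeks (Section 7.1.2.2), adverse events are asked about at each visit (Section 7.2), Grade 1 change needs no intervention (Table 6), and hypothyroidism can be managed with replacement while pembrolizumab continues (Table 3).

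Most of this stands, and it limits the size of the point. It does not remove it. Permission to test when clinically necessary is the third part of Section 5.4.1, not the second. The monitoring instruction also begins before any event, so it is surveillance, which only a schedule delivers uniformly.

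Three stronger readings are tempting, and the documents do not support them.

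- **A QT hazard.** Exclusion criterion 12 names uncontrolled hypothyroidism among conditions that could prolong QT, and ECGs are routine only at screening and EOT. But this is an eligibility rule. Nothing ties on-treatment thyroid change to ECG monitoring, and ECGs are also done when clinically indicated.
- **A thyroid omission specific to the Second Course.** Section 5.2.3 says "All subjects who stop pembrolizumab treatment with CR may be eligible for up to an additional 12 months (17 cycles) of pembrolizumab treatment", and Section 7.1.2.7.1 sets only imaging, starting with "Tumor imaging must be performed within 4 weeks prior to restarting treatment with pembrolizumab". That phase has no laboratory schedule of its own at all, so the gap there is general. Re-entry also requires meeting none of the exclusion safety parameters.
- **A count of missed cases.** Multiplying 57 patients by 7.2% gives about 4.1 hypothyroid events. That is a count of reported events expected to occur. It says nothing about how many this schedule would find late or miss.

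**Conclusion.** The point holds as an inconsistency in the safety schedule. Section 5.4.1 asks for periodic thyroid monitoring, and the schedule provides no routine test during up to 35 cycles of pembrolizumab.

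The consequence is limited to later or uneven detection of early or asymptomatic dysfunction, with possible undercounting of thyroid abnormalities in the safety tables. It can matter for an individual patient through the Table 3 rules for Grade 3 and Grade 4 hyperthyroidism. The response rate is unaffected. So is the toxicity definition in Section 3.2, which counts treatment-related death and Grade 3 or higher hematological toxicity.

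The conclusion rests on reading periodic testing and clinically indicated testing as separate requirements, as Section 5.4.1 lists them. The number of patients affected cannot be derived from the documents, and they do not settle the right interval. The change is worth making because it is cheap and makes the schedule carry out the protocol's own instruction.

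**What to change.** Leave Section 5.4.1 and the screening test as they are. Amend footnote e, Section 7.1.3 and the flow chart so that TSH, free T4 and total T3 are measured at screening, at a stated interval during pembrolizumab, at EOT, and when clinically indicated. Every second cycle from Cycle 3 (Day 59) is an example for the clinical team to confirm. State that the same interval applies if a patient enters the Second Course.

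**Cost.** At every second cycle this adds at most 18 panels per patient in the initial course, and fewer for patients who progress early. The range is 9 (every fourth cycle) to 35 (every cycle). No extra visit or venipuncture is needed in the initial course, because chemistry is already drawn every 3 weeks and at EOT. In the Second Course this is true only if the 3-weekly draw continues, which the protocol should say. More asymptomatic Grade 1 abnormalities will be recorded, and some will prompt a repeat test.

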5.5 Diet/Activity/Other Considerations

5.5.1 Diet

Subjects should maintain a normal diet unless modifications are required to manage an AE such as diarrhea, nausea, or vomiting.

5.5.2 Contraception

Pembrolizumab may have adverse effects on a fetus *in utero*. Furthermore, it is not known if pembrolizumab has transient adverse effects on the composition of sperm.

For this trial, male subjects will be considered to be of non-reproductive potential if they have azoospermia (whether due to having had a vasectomy or due to an underlying medical condition).

Female subjects will be considered of non-reproductive potential if they are either:

- (1) postmenopausal (defined as at least 12 months with no menses without an alternative medical cause; in women < 45 years of age, a high follicle stimulating hormone (FSH) level in the postmenopausal range may be used to confirm a postmenopausal state in women not using hormonal contraception or hormonal replacement therapy. In the absence of 12 months of amenorrhea, a single FSH measurement is insufficient.);

OR

- (2) have had a hysterectomy and/or bilateral oophorectomy, bilateral salpingectomy, or bilateral tubal ligation/occlusion at least 6 weeks prior to screening;

OR

- (3) have a congenital or acquired condition that prevents childbearing.

Female and male subjects of reproductive potential must agree to avoid becoming pregnant or impregnating a partner, respectively, while receiving study treatment and for 120 days after the last dose of study treatment by complying with one of the following:

- (1) practice abstinence[†] from heterosexual activity;

OR

- (2) use (or have their partner use) acceptable contraception during heterosexual activity.

Acceptable methods of contraception are[‡]:

Single method (one of the following is acceptable):

- intrauterine device
- vasectomy of a female subject's male partner
- contraceptive rod implanted into the skin

Combination method (requires use of two of the following):

- diaphragm with spermicide (cannot be used in conjunction with cervical cap/spermicide)
- cervical cap with spermicide (nulliparous women only)
- contraceptive sponge (nulliparous women only)

- male condom or female condom (cannot be used together)
- hormonal contraceptive: contraceptive skin patch, vaginal contraceptive ring, or subcutaneous contraceptive injection

†Abstinence (relative to heterosexual activity) can be used as the sole method of contraception if it is consistently employed as the subject's preferred and usual lifestyle and if considered acceptable by local regulatory agencies and Ethic Review Committees (ERCs)/IRBs. Periodic abstinence (e.g., calendar, ovulation, sympto-thermal, post-ovulation methods, etc.) and withdrawal are not acceptable methods of contraception.

Subjects should be informed that the trial therapy may involve unknown risks to the fetus (unborn baby) if pregnancy were to occur during the study. In order to participate in the study, subjects of childbearing potential must adhere to the contraception requirement (described above) from the day of trial therapy initiation throughout the study period up to 120 days after the last dose of trial therapy. If there is any question that a subject of childbearing potential will not reliably comply with the requirements for contraception, that subject should not be entered into the study.

5.5.3 Use in Pregnancy

If a subject inadvertently becomes pregnant while on the study treatment, the subject will immediately be removed from the study. The site will contact the subject at least monthly and document the subject's status until the pregnancy has been completed or terminated. The outcome of the pregnancy will be reported to the Sponsor and to Merck without delay and within 24 hours to the Sponsor and within 2 working days to Merck if the outcome is a serious adverse experience (e.g., death, abortion, congenital anomaly, or other disabling or life-threatening complication to the mother or newborn).

The study investigator will make every effort to obtain permission to follow the outcome of the pregnancy and report the condition of the fetus or newborn to the Sponsor. If a male subject impregnates his female partner, the study personnel at the site must be informed immediately and the pregnancy reported to the Sponsor and to Merck and followed as described above and in Section 7.2.2.

5.5.4 Use in Nursing Women

It is unknown whether pembrolizumab and valacyclovir are excreted in human milk. It is known, however, that among women taking valacyclovir, concentrations of valacyclovir in breast milk are about four times higher than in the mother's blood. The safety of valacyclovir in breastfeeding infants has not been established. Since many drugs are excreted in human milk, and because of the potential for serious adverse reactions in the nursing infant, subjects who are breastfeeding are not eligible for enrollment.

